14.3.3 Key Elements of the Analysis Plan

Complete details of the analysis plan will be provided in the Statistical Analysis Plan (SAP). Any deviations from, or additions to, the original analysis plan in this protocol will be documented in the SAP and the CSR.

Since it is anticipated that accrual will be spread thinly across centers and summaries of data by center would be unlikely to provide valuable information, data from all participating centers will be pooled prior to analysis.

All data up to the time of study completion/withdrawal from the study will be included in the analysis, regardless of treatment duration.

Since the duration of study treatment for a given subject will depend on efficacy and tolerability, the duration of follow-up will vary among subjects. All available time-to-event data will be analyzed using appropriate statistical methods. Subjects with shorter treatment and follow-up will not be considered to have missing data. Consequently, there will be no imputation for missing time-to-event data.

Demographics and baseline characteristics will be summarized by dose level and cohort(s) within study part and overall.

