14.5.3 Adverse Events

Treatment-emergent adverse events (TEAEs) are defined by applying treatment-emergent signs and symptoms (TESSs) philosophy. AEs will be regarded as TEAEs if one of the following conditions is met:

- Emerge after the time of the administration of the first dose, having been absent prior to the first dose.
- Re-emerge, having been present but stopped prior to the time of the administration of the first dose.
- Worsen in severity after the time of first dose administration relative to the pre-treatment state, when the AE is continuous.

An AE with partial or completely missing start date and/or time will always be assumed as TEAE, unless it can be determined to be “prior to administration” from the incomplete start date/time or resolution date/time (e.g., month, year is before first administration date, or resolution date is before date of first administration).

Only TEAEs will be summarized. Summaries of TEAEs will consist of the number and percentage of subjects reporting the AE by SOC and by PT. TEAEs which occur more than once for a subject will be counted only once in the subject frequencies. TEAEs with different CTCAE grades for a subject will be counted at the worst (highest) grade for the same SOC (likewise for PT). TEAEs with different drug relationship for a subject will be counted at strongest relationship for the same SOC (likewise for PT). TEAEs with missing relationship to study treatment will be counted as “related”. TEAEs with missing CTCAE grade will be counted as Grade 3 (“severe”).

Summaries of TEAEs by study cohort and overall will be produced to present the number and percentage of subjects with:

- Any TEAE
- Any treatment-related TEAE
- Any TEAE with CTCAE Grade 3 or higher
- Any TEAE leading to study treatment discontinuation
- Any Serious TEAEs
- Any TEAE of special interest

Listings will be provided for the following:

- AEs
- TEAEs leading to study treatment discontinuation
- Serious TEAEs
- Fatal TEAEs
- TEAEs of special interest

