3.2. CHANGES TO ANALYSES FROM PROTOCOL

- Section 14.5.4 of the protocol indicates that laboratory analytes will be summarized descriptively as value and change from baseline, as well as shifts from baseline (based on low, normal, high categorization) at each visit. To allow for more focused presentation of values most likely to represent a safety concern, laboratory analytes will be summarized as shift from the baseline to the worst post-baseline category (based on National Cancer Institute [NCI] Common Terminology Criteria for Adverse Events [CTCAE] v 4.03 severity grades).
- In the protocol, PFS is to be summarized using 90% and 95% CIs. However, to be consistent and following standard analyses, PFS will be summarized using % CIs.
- In the protocol, ORR is to be summarized using 80%, 90% and 95% CIs. However, to be consistent and following standard analyses, ORR will be summarized using 95% CIs. In addition, it was indicated that the 95% CI would be done only for expansion phase cohorts with at least 20 patients, however the 95% CI would be provided for all expansion phase cohorts.
- No subgroup analyses were planned in the protocol, however, to assess the possible effect of tazemetostat on previously irradiated lesions, a subgroup analysis of ORR by prior radiotherapy

(Yes vs No) will be performed for the expansion phase by cohort and overall, and for the entire study by dose level and overall.

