7. STATISTICAL CONSIDERATIONS

Unless noted otherwise, the statistical considerations below will be applied. Data from all centers will be pooled for analyses.

- The issue of statistical multiplicity will not apply to this study.
- CIs will be presented as 2-sided 80% and 90% CIs, where noted in subsequent sections.

- Safety data will not be imputed except for incomplete dates associated with AEs and medications (rules in Appendix 1) and missing severity or relationship (rules in Section 17.1).
- Missing response data will be handled as described in Section 15.
- Summary statistics will include the number and percentage of patients in each category for discrete variables and the sample size, mean, median, standard deviation (SD), minimum, and maximum for continuous variables.
- When the denominator includes subjects with missing values, a “missing” category may be added for completeness and displayed last in the category summary.
- Time-to-event statistics will include the minimum, 25th percentile, median, 75th percentile, and maximum, provided they are estimable.
- All mean, median, and quartile values will be formatted to one more decimal place than the measured value. SD values will be formatted to two more decimal places than the measured value.
- The number and percentage of responses will be presented in the form xx (xx.x%) with percentage rounded to one decimal place.
- Change from baseline = post baseline value – baseline value
- Duration in days = end date – start date + 1 (divide by 7 to convert to weeks, divide by 30.44 to convert to months, and divide by 365.25 to convert to years; round result to 1 decimal place
- Listings typically will be sorted by study part, dose level / cohort, subject identification number (concatenated site and subject number), date, and time, if collected.

All analyses will be conducted using SAS version 9.4 or higher.

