17.1. ADVERSE EVENTS

Verbatim AEs terms will be coded using the Medical Dictionary for Regulatory Activities (MedDRA) version in effect at the time of the analysis. Summary tables will be based on treatment emergent adverse events (TEAEs) which are defined as AEs that started or worsened

in severity on or after the day of the first dose of study drug through 30 days after the end of study drug. Missing or partially missing start and end dates for AEs and SAEs will be handled according to the conventions described in Appendix A. For cases in which it is not possible to ascertain treatment-emergence, the event will be classified as treatment-emergent. All AEs, treatment emergent or otherwise, will be presented in subject data listings.

Each summary table will include the incidence (number and percentage) of subjects reporting any TEAE, as well as, by SOC and PT. A subject will be counted once within an SOC, even if the subject experienced more than one TEAE within a specific SOC (likewise for PT).

Investigator assessed severity grade will be based on the National Cancer Institute CTCAE, version 4.03. For summary purposes, TEAEs with a missing severity will be classified as missing. A subject will be counted once at the worst severity grade within a SOC and/or PT.

Investigator assessed causality to study drug will be categorized as “not related,” “unlikely related,” “possibly related,” or “related” to study drug. For summary purposes, treatment-related TEAEs will include events with relationship to study drug classified as “possibly related” or “related”. A TEAE with a missing causality will be classified as “possibly related” to study drug. A subject will be counted once at the strongest causality within a SOC and/or PT.

TEAEs of special interest are defined in Section 10.4 of the protocol. In consultation with study clinicians, this subset of TEAEs will be identified using MedDRA terms.

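### SAP 17.1 leaves adverse events without a grade as missing, while the protocol counts them as Grade 3; SAP 3.2 does not list the change and SAP 7 contradicts it

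*SAP*

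**What the plan says.** **Missing grade.** Protocol 14.5.3: "TEAEs with missing CTCAE grade will be counted as Grade 3", that is, as severe. SAP 17.1: "TEAEs with a missing severity will be classified as missing".

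**Missing relationship.** Protocol 14.5.3: "TEAEs with missing relationship to study treatment will be counted as" related. SAP 17.1: "A TEAE with a missing causality will be classified as" possibly related, a category that the SAP includes among treatment-related events.

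**Imputation of safety data.** SAP 7 rules out imputing safety data, with named exceptions. One is "missing severity or relationship (rules in Section 17.1".

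**Declaring changes.** Protocol 14.3.3: "Any deviations from, or additions to, the original analysis plan in this protocol will be documented in the SAP and the CSR". SAP 3.2, headed "CHANGES TO ANALYSES FROM PROTOCOL", has four items: the form of the laboratory summaries, the confidence level for PFS, the confidence level and coverage for ORR, and an added ORR subgroup by prior radiotherapy. None concerns adverse event grade.

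**Outputs that depend on grade.** The protocol summarises subjects with "Any TEAE with CTCAE Grade 3 or higher". SAP 17.1 has overview rows and tables by system organ class and preferred term for Grade 3 or 4 TEAEs, for all such events and for treatment-related ones. It presents them by study part and overall.

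**The concern.** The protocol sets two conservative defaults side by side: a missing relationship counts as related, and a missing grade counts as severe. The SAP keeps the first in substance and drops the second. It gives no reason and does not label the difference as a change.

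Safety and tolerability is a secondary objective for all subjects, and Protocol 1.5.1 says the study is meant to characterise the pediatric safety profile. The share of subjects with a Grade 3-4 event is a main figure for that purpose. A reader who holds the protocol and checks SAP 3.2 for differences would assume that the Grade 3-4 tables were built under the protocol's rule. They would not be, and the difference can go in only one direction.

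**Working it through.** The plan states no figure on this point, so there is nothing to reproduce. The check is a comparison of texts, followed by an illustration of size.

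**1. Rules compared**

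| Item | Protocol 14.5.3 | SAP 17.1 | Listed in SAP 3.2? |
|---|---|---|---|
| Missing grade | Grade 3 | missing | no |
| Missing relationship | related | possibly related, so treatment-related | no, but same effect on the treatment-related count |

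Both grade rules govern summaries of the same events, and both cannot be followed.

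**2. Consistency within the SAP.** SAP 7 names missing severity as an exception to its no-imputation rule and points to 17.1 for the method. SAP 17.1 has a method for relationship but none for severity. The two sections do not agree.

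**3. Direction.** Let A be the subjects with at least one TEAE graded 3 or 4, and B the subjects with an ungraded TEAE and no TEAE graded 3 or 4. The SAP rule counts A; the protocol rule counts A + B. Since B is at least zero, the SAP count is equal or lower. The same holds within each system organ class or preferred term row and within the treatment-related tables. There, a row can change even for a subject who has a graded Grade 3-4 event elsewhere.

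**4. Worst grade.** SAP 17.1 counts a subject once at the worst grade but does not say where a missing grade ranks. If it ranks lowest, a subject with a Grade 1 event and an ungraded event under the same term appears as Grade 1. Under the protocol rule the same subject appears as Grade 3.

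**5. Size.** Shift in the share of subjects with a Grade 3-4 TEAE = k/N, where k is the number of subjects in B.

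- N is planned enrolment from Protocol 4.1: 48 in dose escalation, 72 in dose expansion, 120 overall. These match the by-study-part and overall units of SAP 17.1.
- k is not given in the documents. I assume 0 to 3.

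| N | k=0 | k=1 | k=3 |
|---|---|---|---|
| 48 | 0 | 1/48 = 2.1 points | 3/48 = 6.3 points |
| 72 | 0 | 1/72 = 1.4 points | 3/72 = 4.2 points |
| 120 | 0 | 1/120 = 0.8 points | 3/120 = 2.5 points |

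If a column for a 20-subject cohort were shown, the range would be 0 to 3/20 = 15 points. SAP 17.1 does not plan that layout for adverse events. The general grouping rule in SAP 6.1 and the by-cohort summaries in Protocol 14.5.3 mean that it cannot be excluded.

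**The case against.** The strongest reply is that little turns on this.

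- **Missing grades should be rare.** Protocol 10.6 requires every event to be graded. Sections 13, 16.2 and 16.3 provide edit checks, queries, monitoring of the case report forms and return of missing data to sites. This stands, and it is why the range must start at zero.
- **Many affected subjects would be counted anyway.** Protocol 1.4.2 reports Grade 3 or 4 events in 52% of subjects with TEAEs across the adult and pediatric program. A subject who already has such an event does not change the overview row. This also stands, although individual term rows can still change.
- **The protocol's rule has its own bias.** It counts an ungraded event as severe even when the event was mild. So the SAP rule is lower than the protocol rule, but not necessarily lower than the truth. That is correct.
- **A SAP may change a descriptive convention, and nothing obliges missing grade and missing relationship to be handled alike.** True, but Protocol 14.3.3 asks for the deviation to be documented, and SAP 3.2 covers changes as small as a confidence level.

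A reader might infer two stronger things that the documents do not support.

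1. *Ungraded events vanish from the safety report.* They do not. They stay in the any-TEAE, treatment-related, serious, dose-interruption, dose-reduction, discontinuation and special-interest tables where they qualify, and SAP 17.1 lists all adverse events. SAP 7 also allows a missing category to be displayed.
2. *The change is concealed.* It is not. SAP 17.1 states the rule openly. The defect is that it is not identified as a departure from the protocol and that SAP 7 says otherwise.

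**Conclusion.** The point holds as a discrepancy that should be corrected. The SAP replaces a pre-specified rule for missing grades, does not list the replacement where changes are declared, and contradicts its own Section 7. These three facts do not depend on the data.

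The numerical effect is unknown and may be zero. Under the assumption of 0 to 3 affected subjects and the planned numbers, it is at most 6.3 points in dose escalation, 4.2 in dose expansion and 2.5 overall, always downward relative to the protocol rule. The 15-point figure applies only to a 20-subject cohort column with three affected subjects, and should not be read as the expected effect.

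ORR, the error rates and the sample size are untouched.

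**What to change.** In SAP 17.1, replace the sentence on missing severity with the protocol's rule (a missing grade is counted as Grade 3), and footnote each Grade 3-4 table with the number of events and subjects imputed. This also brings 17.1 into line with SAP 7 and settles where an ungraded event ranks when the worst grade is taken.

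If the sponsor prefers to leave such grades missing, then:

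- add the change to SAP 3.2 with a reason;
- remove severity from the imputation exceptions in SAP 7;
- say in 17.1 how a missing grade ranks;
- report the Grade 3-4 counts under the protocol rule as a sensitivity summary.

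The preferred change costs about one sentence plus a footnote, best made before database lock. The reported Grade 3-4 rate may be slightly higher, and some of that increase may come from events that were in fact mild; the footnote lets a reader judge this. The change does not by itself restore the protocol's Grade 3-or-higher summary, because SAP 17.1 moves Grade 5 events to the death tables.

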2 OBJECTIVES AND ENDPOINTS

Objectives	Endpoints
Primary: Dose Escalation	

 To determine the MTD or the RP2D of tazemetostat when administered as an oral suspension BID in pediatric subjects with relapsed/refractory rhabdoid tumors, INI1-negative tumors, or synovial sarcoma 	
 Incidence and severity of TEAEs qualifying as protocol-defined DLTs in Cycle 1 Establishment of the protocol-defined RP2D and/or MTD
Primary: Dose Expansion	

 To evaluate the antitumor activity of tazemetostat as assessed by overall response rate (ORR) in in pediatric subjects with relapsed/refractory atypical teratoid rhabdoid tumor (ATRT) (Cohort 1), non-ATRT rhabdoid tumors (Cohort 2), INI1-negative tumors (Cohort 3), and tumor types eligible for Cohorts 1 through 3 or synovial sarcoma with SS18-SSX rearrangement (Cohort 4) using disease-appropriate standardized response criteria 	
 ORR: CR + PR for each cohort
Secondary: Dose Escalation	

 To evaluate the preliminary antitumor activity of tazemetostat as assessed by ORR, using disease-appropriate standardized response criteria 	
 ORR: CR + PR
Secondary: Dose Expansion	

 To determine the PFS and overall survival (OS) at 24 and 56 weeks and overall pediatric subjects with relapsed/refractory ATRT (Cohort 1), non-ATRT rhabdoid tumors (Cohort 2), INI1-negative tumors (Cohort 3), and tumor types eligible for Cohorts 1 through 3 or synovial sarcoma with SS18-SSX rearrangement (Cohort 4) using disease-appropriate standardized response criteria 	
 PFS at 24 and 56 weeks and overall for each cohort OS at 24 and 56 weeks and overall for each cohort
Secondary: All Subjects	

 To assess the safety and tolerability of tazemetostat administered as an oral suspension BID and tablet three times daily (TID) 	
 AEs, clinical laboratory tests, and other safety measures

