6.3 Dose-Limiting Toxicity (DLT)

A DLT will be determined in the first treatment cycle only (Day 1 to Day 28) of dose escalation and will be graded according to the CTCAE version 4.03. A DLT will be defined as a significant adverse reaction (with the exception of tumor progression) that occurred any time from the initial dose of study treatment through the end of the first cycle of treatment in dose escalation that meets any of the following criteria:

- **Non-hematologic toxicity:** any other Grade 3 or greater **non-hematologic** toxicity except:
 - alopecia
 - fatigue/asthenia
 - transient myalgia/arthralgia
 - Grade 3 vomiting or diarrhea that resolves to \leq Grade 2 within 48 hours (with or without supportive care)
 - Grade 3 nausea that resolves (with or without supportive care) to \leq Grade 2 within 7 days
 - Grade 3 anorexia requiring enteral or parenteral nutrition
- **Hematologic toxicity:** myelosuppression, defined as:
 - Grade 4 thrombocytopenia of any duration (by CTCAE, version 4.03) or Grade 3 thrombocytopenia with bleeding or lasting >7 days
 - Grade 4 neutropenia for five consecutive days (by CTCAE, version 4.03)
- Treatment delay of more than 14 days due to delayed recovery from a toxicity related to treatment with tazemetostat

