10.1.2 Serious Adverse Event (SAE)

An SAE is any untoward medical occurrence that, at any dose:

- Results in death
- Is life threatening
- **NOTE:** The term 'life threatening' in the definition of 'serious' refers to an event in which the subject was at risk of death at the time of the event. It does not refer to an event, which hypothetically might have caused death, if it were more severe.
- Requires hospitalization or prolongation of existing hospitalization
NOTE: In general, hospitalization signifies that the subject has been detained (usually involving at least an overnight stay) at the hospital or emergency ward for observation and/or treatment that would not have been appropriate in the physician’s office or

out-patient setting. Complications that occur during hospitalization are AEs. If a complication prolongs hospitalization or fulfills any other serious criteria, the event is serious. When in doubt as to whether “hospitalization” occurred or was necessary, the AE should be considered serious.

Hospitalization for elective treatment of a pre-existing condition that did not worsen from baseline is not considered an AE.

- Results in disability/incapacity, or

NOTE: The term disability means a substantial disruption of a person’s ability to conduct normal life functions. This definition is not intended to include experiences of relatively minor medical significance such as uncomplicated headache, nausea, vomiting, diarrhea, influenza, and accidental trauma (e.g., sprained ankle) which may interfere or prevent everyday life functions but do not constitute a substantial disruption.

- Is a congenital anomaly/birth defect.
- Medical or scientific judgment should be exercised in deciding whether reporting is appropriate in other situations, such as important medical events that may not be immediately life threatening or result in death or hospitalization but may jeopardize the subject or may require medical or surgical intervention to prevent one of the other outcomes listed in the above definition. These should also be considered serious. Examples of such events are intensive treatment in an emergency room or at home for allergic bronchospasm, blood dyscrasias or convulsions (in subjects without pre-existing seizure disorder) that do not result in hospitalization, or development of drug dependency or drug abuse.

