An overview summary table of subjects with TEAEs will be provided by study part and overall and will include the number of subjects with any TEAE, any TEAE Grade 3 or 4, any TEAE DLT (as defined in the protocol Section 6.3), any treatment-related TEAE, any treatment-related TEAE Grade 3 or 4, any TEAE leading to dose reduction, any TEAE leading to study drug interruption, any TEAE leading to discontinuation of study drug, any TEAE leading to study discontinuation, any serious TEAE (TESAE), any treatment-related TESAE, any protocol defined TEAE of special interest. In accordance with the TEAE table presentation described above, AEs will be summarized by study part and overall as follows:

- TEAEs
- TEAEs with $\geq 10\%$ incidence overall based on PT
- TEAEs of grade 3 or 4
- Treatment-related TEAEs
- Treatment-related TEAEs of grade 3 or 4
- TEAEs leading to dose interruption
- TEAEs leading to dose reduction

- TEAEs leading to discontinuation of study drug
- TEAEs leading to discontinuation from study
- Treatment-emergent serious adverse events (SAEs)
- Treatment-related treatment emergent SAEs
- TEAEs of special interest
- DLTs

Additionally, separate listings of DLTs, SAEs, , TEAEs leading to discontinuation of study drug and TEAEs leading to dose modifications (interruption and dose reduction). A listing of TEAEs of special interest will be also provided.

Adverse events with CTCAE Grade 5 or outcome of death are excluded from AE summary tables and summarized under death related tables.

Deaths

Deaths will be summarized and listed as follows:

- Summary and listing of subjects who died during and till 30 days after last dose of study drug
- Summary and listing of subjects who died during and till 30 days after last dose of study drug with treatment-related TEAEs
- Summary and listing of subjects who died after 30 days after the last dose of study drug with treatment-related AEs

The summary and listing will include the reason for death:

- Any AE (by MedDRA preferred Term)
- Any treatment related TEAE
- Progression
- Tumor progression
- Disease under Study

- Unknown/Other causes

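### SAP 17.1 takes fatal AEs out of the AE tables and no longer counts a missing grade as Grade 3, both undeclared; its TEAE cut-off also removes late AESIs from the AESI table and listing

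*SAP*

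**What the plan says.** Protocol 14.3.3 sets the duty to declare: "Any deviations from, or additions to, the original analysis plan in this protocol will be documented in the SAP and the CSR". SAP 3.2 is where those changes are recorded. Its only safety entry concerns laboratory data: "laboratory analytes will be summarized as shift from the baseline to the worst post-baseline category". The other entries cover PFS and ORR confidence intervals and a radiotherapy subgroup. No entry concerns adverse events.

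**Fatal events.** SAP 17.1: "Adverse events with CTCAE Grade 5 or outcome of death are excluded from AE summary tables and summarized under death related tables". The AE summaries listed in that section include all, treatment-related, serious, special-interest and discontinuation TEAEs, and DLTs. Its severity rows are limited to Grades 3 and 4. Protocol 14.5.3 has a row for "Any TEAE with CTCAE Grade 3 or higher" and adds a listing of fatal TEAEs; it excludes nothing from the tables.

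**Missing grade.** Protocol 14.5.3 counts it as Grade 3. SAP 17.1 reports it as missing.

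**End of the TEAE period.** The protocol 14.5.3 definition has none. SAP 17.1 stops 30 days after study drug. SAP Appendix 1 stops at that point or at new anti-cancer therapy, whichever is sooner.

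**The concern.** The serious, high-grade, AESI and DLT tables are where a reader looks for the gravest events. Protocol 10.1.2 makes "Results in death" the first seriousness criterion, so a serious-event table that leaves out fatal events drops cases that are serious by definition. The non-hematologic part of the DLT definition in protocol 6.3 covers "any other Grade 3 or greater" toxicity with no upper limit, and the escalation primary endpoint in protocol 2 is "Incidence and severity of TEAEs qualifying as protocol-defined DLTs in Cycle 1". A fatal DLT would therefore be missing from the summary of a primary endpoint.

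The missing-grade change can only lower Grade 3 or higher counts. The cut-off matters because secondary malignancy is the central long-term safety question here. Protocol 9.4 collects AESIs for as long as survival is followed, and protocol 10.9 asks for secondary lymphoma to be reported beyond 30 days. A case that arises then would be collected but not counted.

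**Working it through.** **1. The texts side by side**

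| Point | Protocol | SAP | In SAP 3.2? |
|---|---|---|---|
| Fatal AEs | 14.5.3: in the tables, plus a fatal listing | 17.1: out of AE tables, into death tables | No |
| High-grade row | 14.5.3: Grade 3 or higher | 17.1: Grade 3 or 4 | No |
| Missing grade | 14.5.3: Grade 3 | 17.1: missing | No |
| TEAE end | 14.5.3: none | 17.1: 30 days; Appendix 1: 30 days or new therapy | No |

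The SAP also contradicts itself twice. SAP 7 names missing severity as an exception that is imputed under 17.1, but 17.1 imputes nothing for it. An event that starts within 30 days of study drug but after new therapy is a TEAE under 17.1 and not under Appendix 1. Missing relationship is still counted as related in both documents, so the grade change stands alone.

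**2. Do the death tables make up the loss?** Mostly. SAP 17.1 has three death summaries: deaths on treatment or within 30 days; the same deaths with treatment-related TEAEs; and "Summary and listing of subjects who died after 30 days after the last dose of study drug with treatment-related AEs". Take an AE that starts in the TEAE window, is judged unrelated, and leads to death more than 30 days after last dose. Its fatal outcome removes it from the AE tables. The first two death summaries do not reach that date, and the third needs a treatment-related AE. Unless the subject also had one, the death is in no AE or death summary. The event remains in the subject listings.

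**3. Late AESIs and related SAEs.** For routine AEs the SAP window is close to the collection window in protocol 10.9, so little is lost. The loss is confined to AESIs (collected through survival follow-up) and related SAEs (recorded up to any follow-up contact). Late ones leave the AESI and serious tables. Late AESIs also leave the AESI listing, which is limited to TEAEs. Serious ones should still appear in the SAE listing, and all AEs appear in the general listings.

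**4. Bound on fatal events.** Protocol 1.4.2 gives 25 (28%) deaths in this study at 24 May 2019, and protocol 1.6.5 gives 90 treated subjects. 25/90 = 27.8%, which reproduces the stated 28%. I read the 25 as deaths on treatment or within 30 days, as in the rest of that sentence. The number with a fatal AE record is not given, so the range is 0/90 = 0% to 25/90 = 27.8%. Later deaths are outside this bound.

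**5. Direction.** Within one preferred term a subject can show any non-empty set of {1, 2, 3, 4, 5, missing}: 2^6 − 1 = 63 sets. I compare the protocol rule (missing = 3, Grade 5 kept) with the SAP rule (Grade 5 removed, missing left missing).

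- Any TEAE: 63 against 62. Only the set {5} is lost and none is gained.
- Grade 3 or higher: under the protocol, all sets except the 3 drawn from {1, 2} alone, so 63 − 3 = 60. Under the SAP, sets containing 3 or 4: 64 − 16 = 48. The fall is 60 − 48 = 12, with no gain.
- Worst grade 3 or 4: sets with a 5 and also a 3 or 4 move in (24). Sets with a missing grade and no 3, 4 or 5 move out (4).

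With the fatal rule alone (31 sets of grades 1 to 5), Grade 3 or higher falls in 4 and rises in 0, and the Grade 3–4 cell rises in 12. These are combinations, not frequencies. The SAP also counts events on the day of first dose, where the protocol counts from the time of dosing; that can add an event and is outside this comparison.

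**The case against.** The case for leaving this alone has six parts.

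- **Fatal events are relocated, not hidden.** They appear in death tables with the reason by preferred term, in the SAE listing, and through deaths in OS. This is true, apart from the class in step 2. It does not make the serious and high-grade tables complete.
- **No fatal DLT is documented.** Protocol 1.5.2.2 reports no DLTs at 1200 mg/m², and the only two deaths that protocol 1.4.2 names as possibly treatment-related were in adults. This stands: no effect on the escalation result is shown, and the fault is in the table rule.
- **27.8% is a ceiling.** Protocol 10.3.1 says progression itself is not an SAE, and 129 of 135 programme deaths were attributed to disease. That leaves 135 − 129 = 6. If the two adult cases are among them, at most 4 could be pediatric (4/90 = 4.4%). However, 10.3.1 also has serious events associated with progression reported as SAEs, so a disease-attributed death can carry a fatal AE. The ceiling holds, but only as a ceiling.
- **The enumeration omits lower-graded events with a fatal outcome.** This is correct. Removing those as well could only lower the any-TEAE and Grade 3 or higher counts, so the direction is unchanged.
- **Protocol 14.5.3 itself asks for TEAEs of special interest.** It does, but its TEAE definition has no end date. An AESI summary through follow-up is nevertheless an addition to the protocol and has to be declared as one.
- **Missing grades will be queried before database lock.** Probably so, which makes the change small. It remains undeclared and inconsistent with SAP 7.

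**Conclusion.** The concern holds and should be fixed. Followed as written, the SAP produces serious, high-grade, AESI and DLT tables that can omit fatal or late events, and one narrow class of deaths that no AE or death summary captures. The departures on fatal events, missing grade and the TEAE end date are undeclared, despite protocol 14.3.3.

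Confidence in the textual mismatch is high. Its numerical effect is unknown: the documents give no count of fatal AEs, missing grades or late AESIs. The only figure available is the 0 to 27.8% bound, which rests on reading the 25 deaths as falling on treatment or within 30 days. For any TEAE and for Grade 3 or higher, the fatal and missing-grade rules can lower a count and cannot raise it. The worst-grade 3–4 cell can move either way.

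**What to change.** In SAP 17.1:

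1. Include Grade 5 and fatal-outcome events in the TEAE, treatment-related, serious, discontinuation, AESI and DLT tables. Replace the Grade 3 or 4 rows with Grade 3 or higher. Keep the death tables, with a footnote that fatal events appear in both places.
2. Restore missing grade as Grade 3. Otherwise declare the change in 3.2, show both counts and correct SAP 7.
3. Use one TEAE end date in 17.1 and Appendix 1, assign the boundary day (Appendix 1 leaves it unclassified), and declare it in 3.2.
4. Tabulate and list AESIs and related SAEs through the end of follow-up, with the TEAE-window count as a sub-row. This goes beyond protocol 14.5.3, so it also needs an entry in 3.2.

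The cost is SAP wording, entries in 3.2 and revised table shells on data already collected. The downsides are that fatal events appear in both AE and death tables, and some reported rates may look slightly less favourable.
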